10.3. Appendix 3: Treatment States

10.3.1. Treatment States for AE Data

Assessments and events will be classified according to date of occurrence relative to the start and/or stop date of the study treatment.

Treatment State	Definition
Pre-Treatment	Date < Study Treatment Start Date
On-Treatment	If AE onset date is on or after treatment start date & on or before the treatment stop date + 2 days $\text{Study Treatment Start Date} \leq \text{AE Start Date} \leq \text{Study Treatment Stop Date} + 2 \text{ days}$
Post-Treatment	If AE onset date is after the treatment stop date + 2 days $\text{AE Start Date} > \text{Study Treatment Stop Date} + 2 \text{ days}$
AE Onset Time Since First Dose (Days)	If Treatment Start Date > AE Onset Date = AE Onset Date - Treatment Start Date If Treatment Start Date \leq AE Onset Date = AE Onset Date - Treatment Start Date + 1 day Missing otherwise
AE Duration (Days)	AE Resolution Date – AE Onset Date + 1 day
AE Drug-related	If relationship is marked 'YES' on eCRF or value is missing.

NOTES:

- If the study treatment stop date is missing, then the AE will be considered to be On-Treatment.

10.4. Appendix 4: Data Display Standards & Handling Conventions

10.4.1. Study Display Descriptors

Study Display Descriptions			
Study Part	Cohort		Data display for reporting
	Code	Description	Description ^[2]
1	1	Moderate Hepatic Impairment	Cohort 1
1	2	Matched Healthy Controls for Moderate Hepatic Impairment	Cohort 2
2	3	Mild Hepatic Impairment / Severe Hepatic Impairment ^[1]	Cohort 3
2	4	Matched Healthy Controls for Mild Hepatic Impairment / Matched Healthy Controls for Severe Hepatic Impairment ^[1]	Cohort 4

^[1] Either Mild or Severe Hepatic Impairment participants will be selected based on part 1 results.

^[2] The word "Cohort" may be omitted from displays in order to limit wrapping

10.4.2. Baseline Definition & Derivations

10.4.2.1. Baseline Definitions

For all endpoints (except as noted in [Table 9](#)) the baseline value will be the latest non-missing pre-dose assessment. If there are multiple assessments collected on the same scheduled time, the average of these assessments will be used, unless otherwise stated.

Table 10 Baseline Definitions

Parameter	Study Assessments Considered As Baseline			Baseline Used in Data Display
	Screening	Day -1	Day 1 (Pre-Dose)	
Safety				
12 Lead ECG & Vital Signs	X	X		Day -1
Haematology	X			Screening
Clinical Chemistry	X			Screening
Pharmacodynamic				
EPO blood sampling			X	Pre-Dose

10.4.2.2. Derivations and Handling of Missing Baseline Data

Definition	Reporting Details
Change from Baseline	= Post-Dose Visit Value – Baseline
NOTES : 
 Unless otherwise specified, the baseline definitions specified in Section 10.4.2.1 Baseline Definitions will be used for derivations for endpoints / parameters and indicated on summaries. Unless otherwise stated, if baseline data is missing or post-dose data is missing no derivation will be performed. The baseline definition will be footnoted on all change from baseline displays. 	

10.4.3. Reporting Process & Standards

Reporting Process	
Software	

 The currently supported versions of SAS 9.3 or latest software will be used. 	
Reporting Area	
HARP Server	: UK1SALX00175
HARP Area	: arenv/arprod/GSK1278863/mid200231/final
QC Spreadsheet	: arenv/arwork/GSK1278863/mid200231/final/documents
Analysis Datasets	

 Analysis datasets will be created according to CDISC standards (SDTM IG Version 3.1.3 & AdaM IG Version 1.0). For creation of ADaM datasets (ADCM/ADAE), the same version of dictionary datasets will be implemented for conversion from SI to SDTM. 	
Generation of RTF Files	

 RTF files will be generated only for SAC. 	

Reporting Standards	
General	

 The current GSK Integrated Data Standards Library (IDSL) will be applied for reporting, unless otherwise stated: 
 4.03 to 4.23: General Principles 5.01 to 5.08: Principles Related to Data Listings 6.01 to 6.11: Principles Related to Summary Tables 7.01 to 7.13: Principles Related to Graphics 	
Formats	

 All data will be reported according to the actual treatment the subject received unless otherwise stated. GSK IDSL Statistical Principles (5.03 & 6.06.3) for decimal places (DP's) will be adopted for reporting of data based on the raw data collected. 	

Reporting Standards	

 Numeric data will be reported at the precision collected on the eCRF. The reported precision from non eCRF sources will follow the IDSL statistical principles but may be adjusted to a clinically interpretable number of DP's. 	
Planned and Actual Time	

 Reporting for tables, figures and formal statistical analyses: 
 Planned time relative to dosing will be used in figures, summaries, statistical analyses and calculation of any derived parameters, unless otherwise stated. The impact of any major deviation from the planned assessment times and/or scheduled visit days on the analyses and interpretation of the results will be assessed as appropriate (see Section 4.1). Reporting for Data Listings: 
 Planned and actual time relative to study drug dosing will be shown in listings (Refer to IDSL Statistical Principle 5.05.1). Unscheduled or unplanned readings will be presented within the subject's listings. Visits outside the protocol defined time-windows (i.e. recorded as protocol deviations) will be included in listings but omitted from figures, summaries and statistical analyses. 	
Unscheduled Visits	

 Unscheduled visits will not be included in summary tables, unless otherwise stated. Unscheduled visits will not be included in figures. All unscheduled visits will be included in listings. 	
Descriptive Summary Statistics	
Continuous Data	Refer to IDSL Statistical Principle 6.06.1
Categorical Data	N, n, frequency, %
Reporting of Pharmacokinetic and Pharmacodynamic Concentration Data	
Descriptive Summary Statistics	Refer to IDSL Statistical Principle 6.06.1 and Standards for the Transfer and Reporting of PK and PD Data using HARP. For NQ values, refer to GUI_51487.
Reporting of Pharmacokinetic Parameters	
Descriptive Summary Statistics. (Log _e Transformed)	N, n, geometric mean, 95% CI of geometric mean, standard deviation (SD) of log transformed data and %CVb will be reported. $CVb (\%) = \sqrt{(\exp(SD^2) - 1)} * 100$ [NOTE: SD = SD of log _e transformed data]
Parameters Not Being Log _e Transformed	%AUCex and Tmax
Summary Tables	Cmax, Tmax, AUC(0-t), AUC (0-∞), t1/2, and %AUCex as data permit. The following PK parameters will not be summarised: first point, last point, and number of points used in the determination of λz.
Summary of Statistical analysis	Geometric mean ratio of hepatic impaired : healthy, point estimate and an associated 90% CI.

Reporting Standards	
Listings	Include PK Parameters C _{max} , T _{max} , AUC(0-t), AUC (0-∞), and t _{1/2} as data permit. Include the first point, last point and number of points used in the determination of λ _z .
Reporting of Pharmacodynamic Parameters	
Descriptive Summary Statistics	N, n, arithmetic mean, 95% confidence interval (CI) for the arithmetic mean, SD, median, minimum and maximum
Parameters	C _{max} , EPO, T _{max} , EPO and AUC (0-t, EPO)
Summary Tables	C _{max} , EPO, T _{max} , EPO and AUC (0-t, EPO) as data permit
Listings	Include PD Parameters C _{max} , EPO, T _{max} , EPO and AUC (0-t, EPO) as data permit
Graphical Displays	

 Refer to IDSL Statistical Principles 7.01 to 7.13 and Standards for the Transfer and Reporting of PK and PD Data using HARP. 	

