### 9.5.4. Clinical Safety Laboratory Assessments

- Refer to [Appendix 3](#) for the list of clinical laboratory tests to be performed and to the SoA (Section 2) for the timing and frequency.
- The investigator must review the laboratory report, document this review, and record any clinically relevant changes occurring during the study in the AE section of the CRF. The laboratory reports must be filed with the source documents. Clinically significant abnormal laboratory findings are those which are not associated with the underlying disease, unless judged by the investigator to be more severe than expected for the participant's condition.
- All laboratory tests with values considered clinically significantly abnormal during participation in the study or at the follow-up visit should be repeated until the values return to normal or baseline or are no longer considered significantly abnormal by the investigator or medical monitor.
- If such values do not return to normal/baseline within a period of time judged reasonable by the investigator, the etiology should be identified and the sponsor notified.
- All protocol-required laboratory assessments, as defined in [Appendix 3](#), must be conducted in accordance with the laboratory manual and the SoA.

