## **10.4. Key Elements of Analysis Plan**

Final analyses will be performed after the completion of the study and final dataset authorization.

Data will be listed and summarized separately for each part of the study according to GSK reporting standards where applicable. Listings will be sorted by participant, period, day, and time, noting treatment. Summaries will be presented by treatment, day and time.

Unless stated otherwise, descriptive summaries for continuous variables will include n, mean, standard deviation (SD), coefficient of variation for the mean (%CV), median, minimum, maximum, geometric mean with associated 95% confidence interval (CI), and the between-participant CV (%CVb) for the geometric mean; whereas, n and percent will be used as summary statistics for categorical variables.

Baseline or pre-dose assessment is the last available assessment prior to time of the first dose unless it is specified otherwise. If there are multiple assessments collected on the same scheduled time, the average of these assessments will be used. For tabulated safety summaries, only the scheduled assessments will be included in the summary tables.

Version 9.4 or higher of the SAS system will be used to analyze data as well as to generate tables, listings, and figures.

Complete details will be documented in the Reporting and Analysis Plan (RAP).

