10.10.4. Safety Tables

Safety : Tables					
No.	Population	IDSL / TST ID / Example Shell	Title	Programming Notes	Deliverable [Priority]
Adverse Events					
2.1	Safety	AE1CP	Summary of All Adverse Events by System Organ Class and Preferred Term		DR, SAC
2.2	Safety	AE1CP	Summary of Drug-Related Adverse Events by System Organ Class and Preferred Term		DR, SAC
2.3	Safety	AE1CP	Summary of Adverse Events Leading to Withdrawal from Study		DR, SAC
2.4	Safety	AE1CP	Summary of Serious Adverse Events by System Organ Class and Preferred Term		DR, SAC
2.5	Safety	AE16	Summary of Serious Adverse Events by System Organ Class and Preferred Term (Number of Subjects and Occurrences)		DR, SAC
2.6	Safety	AE15	Summary of Common ($\geq 25\%$) Non-serious Adverse Events by System Organ Class and Preferred Term (Number of Subjects and Occurrences)		DR, SAC
Laboratory Measurements					
2.7	Safety	LB1	Summary of Chemistry Values		DR, SAC
2.8	Safety	LB1	Summary of Chemistry Changes from Baseline		DR, SAC
2.9	Safety	LB17	Summary of Worst Case Chemistry Results Relative to Potential Clinical Importance Criteria Post-Baseline Relative to Baseline		DR, SAC
2.10	Safety	LB1	Summary of Haematology Values		DR, SAC
2.11	Safety	LB1	Summary of Haematology Changes from Baseline		DR, SAC
2.12	Safety	LB17	Summary of Worst Case Haematology Results Relative to Potential Clinical Importance Criteria Post-Baseline Relative to Baseline		DR, SAC

Safety : Tables					
Electrocardiograms					
2.13	Safety	EG1	Summary of ECG Findings		DR, SAC
2.14	Safety	EG2	Summary of ECG Values		DR, SAC
2.15	Safety	EG2	Summary of Change from Baseline in ECG Values		DR, SAC
2.16	Safety	EG10	Summary of Maximum QTc Values Post-Baseline Relative to Baseline by Category		DR, SAC
2.17	Safety	EG11	Summary of Maximum Increase in QTc Values Post-Baseline Relative to Baseline by Category		DR, SAC
Vital Signs					
2.18	Safety	VS1	Summary of Vital Signs		DR, SAC
2.19	Safety	VS1	Summary of Change from Baseline in Vital Signs		DR, SAC

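### The worst-case laboratory and maximum QTc tables use only scheduled, in-window visits, so in four identifiable situations they can miss a participant's true worst value

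*SAP*

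**What the plan says.** Three rules decide which safety data reach a table.

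- SAP 10.4.3, on unscheduled visits: "Unscheduled visits will not be included in summary tables, unless otherwise stated". These visits go to listings.
- SAP 10.4.3, on planned and actual time: "Visits outside the protocol defined time-windows (i.e. recorded as protocol deviations) will be included in listings but omitted from figures, summaries and statistical analyses". This rule has no exception clause.
- Protocol 10.4: "For tabulated safety summaries, only the scheduled assessments will be included in the summary tables". This rule has none either.

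SAP 10.10.4 plans four tables whose titles promise the extreme post-baseline result: Table 2.9, "Summary of Worst Case Chemistry Results Relative to Potential Clinical Importance Criteria Post-Baseline Relative to Baseline"; Table 2.12, "Summary of Worst Case Haematology Results Relative to Potential Clinical Importance Criteria Post-Baseline Relative to Baseline"; Table 2.16, "Summary of Maximum QTc Values Post-Baseline Relative to Baseline by Category"; and Table 2.17, the matching table of the largest QTc increase. Their Programming Notes are blank. Where the SAP does want unscheduled data it says so in that column, but only for Listings 39, 40 and 46 (drug and erythropoietin concentrations).

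The protocol also generates unscheduled values. Under 9.5.4, laboratory results judged clinically significantly abnormal "should be repeated until the values return to normal or baseline or are no longer considered significantly abnormal". Under Appendix 7, a healthy control with ALT of at least 3×ULN has liver chemistry repeated within 24 h or 24-72 h, then twice weekly or weekly.

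**The concern.** A scheduled-only rule is sensible for by-visit summaries, where each column should hold comparable data. It does not suit a table labelled worst case or maximum, because a reader will take that label to mean the worst value observed. If the worst value fell at an unscheduled draw or an off-window follow-up, the table can show no clinically important result while the listing of such values shows one. Safety and tolerability, including clinical laboratory tests, is a secondary objective, and in cohorts of eight a single participant is visible in every percentage.

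**Working it through.** The plan states no figure to reproduce. The check is a comparison of rules, plus two simple counts.

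1. **How many readings feed each table.** The schedule of activities has post-dose laboratory tests and 12-lead ECGs at 48 h and at follow-up, so at most 2 scheduled readings per participant. Follow-up is due 10 to 14 days after the dose. If it takes place 15 days after the dose, the out-of-window rule removes it, leaving 2 − 1 = 1 reading, half of that participant's scheduled post-dose data.

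2. **Is an exception stated?** The SAP rule on unscheduled visits allows for one. The blank Programming Notes do not supply it. SAP 10.5.1 says that a participant with both High and Low values at any post-baseline visit counts in both categories, and extends this to tables of potential clinical importance. That settles how to count, and does not say that unscheduled or off-window data enter. Protocol 10.4 is unqualified.

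3. **What happens to a scheduled abnormal value that triggers a repeat.** It stays in the table. For healthy controls the ALT flag in SAP 10.7.1 is ≥2×ULN and the Appendix 7 trigger is ≥3×ULN. Since 3 > 2, a scheduled trigger is already flagged, and leaving out later, higher repeats cannot remove that flag.

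4. **Where a miss is possible.** Four routes remain:
   - an unscheduled test that no scheduled abnormality prompted (protocol Appendix 3 lets the investigator add tests at any time);
   - a scheduled value below the potential-clinical-importance threshold that prompts a repeat and crosses the threshold only then;
   - a second analyte, or the combined bilirubin and ALT criterion, met only on a repeat;
   - a follow-up visit outside its window.

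5. **Example of the third route.** At 48 h a healthy control has ALT of 3×ULN and bilirubin below 1.5×ULN. On a required repeat, bilirubin reaches 1.5×ULN while ALT is still at least 2×ULN. Both have settled by follow-up. Table 2.9 counts the ALT flag. The bilirubin flag (≥1.5×ULN) and the combined flag (bilirubin 1.5×ULN with ALT ≥2×ULN) were met only at an unscheduled draw and are not counted, although Listings 22 and 23 would show them.

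6. **QTc.** Protocol 9.5.3 asks for two further ECGs when QTc is prolonged, but at the same scheduled time point, so they are not unscheduled visits. For Tables 2.16 and 2.17 only ad hoc ECGs and an off-window follow-up remain.

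7. **Size.** With 8 participants per cohort, one missed participant moves a table category by 1/8 = 12.5 percentage points.

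**The case against.** The strongest reply is that little is at risk. Protocol and SAP agree, so this is a prespecified display convention and not a contradiction. Repeats follow a value already judged significant and continue until it settles, so many will track recovery. Every unscheduled value is listed. Listings 22-25 and 29-30 give values of potential clinical importance and all data for the participants concerned, and Listings 18 and 33-38 cover liver events. With eight per cohort these can be read line by line. SAP 10.4.3 also says the impact of major timing deviations will be assessed. The sponsor's standard table shells (LB17, EG10, EG11) and summary-table principles are not supplied and might already provide for unscheduled data.

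Most of this stands, and it rules out two stronger readings. A reader might infer that the values most likely to be extreme are the ones systematically dropped. Step 3 shows otherwise: the scheduled trigger is retained, and a miss needs one of the four routes. A reader might also infer that a peak between 48 h and follow-up enters no table. Protocol 9.5.4 requires clinically relevant laboratory changes to be recorded as adverse events, and these are tabulated in Table 2.1. A peak that nobody measured is beyond any table rule.

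The reply does not remove the mismatch between the table titles and the stated rule. If the shells do include unscheduled data, they conflict with protocol 10.4, and the text still needs a sentence.

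**Conclusion.** The point holds as a minor one. As written, Tables 2.9, 2.12, 2.16 and 2.17 report the worst scheduled, in-window value, which can differ from the worst observed value by the four routes above. The laboratory tables are more exposed than the QTc tables. No data are lost, and the risk is that a table disagrees with its companion listing. The 12.5 percentage points is the weight of one participant, not an expected frequency: nothing in the documents indicates how often a missed value or a late follow-up would occur. The conclusion assumes that the unseen shells contain no overriding rule and that protocol 10.4 is applied as worded.

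**What to change.** State in SAP 10.4.3, in the Programming Notes of Tables 2.9, 2.12, 2.16 and 2.17, and in protocol 10.4 that worst-case and maximum derivations use all post-dose assessments, whether scheduled, unscheduled or out of window. Keep by-visit tables on scheduled visits, but retain an early or late follow-up under its nominal visit with a flag.

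The cost is a few lines of text and a small programming change. There is one drawback. Appendix 7 liver monitoring applies only to healthy controls, so a control with a liver event would contribute more repeat values to the worst-case search than an impaired participant. Footnote this on the affected tables so that a difference between cohorts is not over-read.

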#### 4. OBJECTIVES AND ENDPOINTS

Objective	Endpoint
Primary	
To compare plasma PK parameters of daprodustat and its six metabolites (GSK2391220 (M2), GSK2506104 (M3), GSK2487818 (M4), GSK2506102 (M5), GSK2531398 (M6), GSK2531401 (M13)) in participants with hepatic impairment to healthy controls matched in gender, age, and body mass index (BMI)	Daprodustat and its metabolites plasma area under the concentration-time curve from time zero (pre-dose) extrapolated to infinite time [AUC(0-∞)], percentage of AUC(0-∞) obtained by extrapolation (%AUC ex ), time zero (pre-dose) to last time of quantifiable concentration [AUC(0-t)], maximum observed concentration (C max ) following a single oral dose of daprodustat, apparent terminal phase half-life (t 1/2 ), and time of occurrence of C max (T max ) following a single oral dose of daprodustat
To evaluate the impact of hepatic impairment on the plasma protein binding and unbound concentration of daprodustat and its metabolites in plasma	Unbound concentration and unbound fraction in plasma of daprodustat and its metabolites at 3, 12 and 24 h post dose (as data permit)
Secondary	
To characterize the effect of hepatic impairment on the pharmacodynamics effect of daprodustat	Maximum observed erythropoietin concentration (C max , EPO), Time of the maximum observed erythropoietin concentration (T max , EPO) and erythropoietin area under the concentration-time curve from time zero (pre-dose) to the last time of quantifiable concentration [AUC (0-t, EPO)].
To assess the safety and tolerability of a single 6 mg dose of daprodustat	Safety and tolerability parameters, including adverse events and clinical laboratory tests

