#### **10.4.2. Pharmacodynamic Analyses**

Pharmacodynamic data will be presented in graphical and/or tabular form and will be summarized descriptively.

Descriptive statistics, where appropriate, (n, arithmetic mean, geometric mean, standard deviation, minimum, median and maximum) will be calculated for the pharmacodynamic endpoints.

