2. SUMMARY OF KEY PROTOCOL INFORMATION

2.1. Study Objective(s) and Endpoint(s)

Objectives	Endpoints

Primary Objectives
 
 To compare plasma PK parameters of daprodustat and its six metabolites (GSK2391220 (M2), GSK2506104 (M3), GSK2487818 (M4), GSK2506102 (M5), GSK2531398 (M6), and GSK2531401 (M13)) in participants with hepatic impairment to healthy controls matched in gender, age, and body mass index (BMI). To evaluate the impact of hepatic impairment on the plasma protein binding and unbound concentration of daprodustat and its metabolites in plasma. 	
Primary Endpoints
 
 Daprodustat and its metabolites plasma area under the concentration-time curve from time zero (pre-dose) extrapolated to infinite time [AUC (0-∞)], percentage of AUC(0-∞) obtained by extrapolation (%AUCex), time zero (pre-dose) to last time of quantifiable concentration [AUC(0-t)], maximum observed concentration (C_{max}) following a single oral dose of daprodustat, apparent terminal phase half-life (t_{1/2}), and time of occurrence of C_{max} (T_{max}) following a single oral dose of daprodustat. Unbound concentration and unbound fraction in plasma of daprodustat and its metabolites at 3, 12 and 24 h post dose (as data permit).

Secondary Objectives
 
 To characterize the effect of hepatic impairment on the PD effect of daprodustat. To assess the safety and tolerability of a single 6 mg dose of daprodustat. 	
Secondary Endpoints
 
 Maximum observed erythropoietin concentration (C_{max}, EPO), Time of the maximum observed erythropoietin concentration (T_{max}, EPO) and erythropoietin area under the concentration-time curve from time zero (pre-dose) to the last time of quantifiable concentration [AUC (0-t, EPO)]. Safety and tolerability parameters, including adverse events and clinical laboratory tests.

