7.3.1.1. Pharmacodynamic Parameters**7.3.1.1.1. Deriving Pharmacodynamic Parameters**

- Although erythropoietin (EPO) is an endogenous substance, the plasma concentrations of erythropoietin will not be corrected for baseline endogenous levels. Pharmacodynamic analysis will be performed on uncorrected (absolute erythropoietin concentrations) data only.
- Maximum observed erythropoietin concentration (C_{max}, EPO), Time of the maximum observed erythropoietin concentration (T_{max}, EPO) and area under the concentration-time curve from time zero (pre-dose) to the last time of quantifiable erythropoietin concentration [AUC (0-t, EPO)] will be listed and summarised if data is available.
- Pharmacodynamic parameters described in [Table 6](#) will be determined from plasma absolute erythropoietin concentration-time data as data permits.

Table 6 Derived Pharmacodynamic Parameters

Parameter	Parameter Description
C _{max} , EPO	Maximum observed EPO concentration
T _{max} , EPO	Time of the maximum observed EPO concentration
AUC (0-t, EPO)	Area under the concentration-time curve from time zero (pre-dose) to the last time of quantifiable erythropoietin concentration

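### The SAP leaves the protocol's geometric mean out of the EPO parameter summaries, and neither document prespecifies an impaired-versus-healthy estimate for the secondary PD objective

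*SAP*

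**What the plan says.** The secondary PD objective in protocol section 4 is "To characterize the effect of hepatic impairment on the pharmacodynamics effect of daprodustat", and SAP 2.1 repeats it. The amended endpoints are Cmax,EPO, Tmax,EPO and AUC(0-t,EPO).

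Protocol 10.4.2 states: "Pharmacodynamic data will be presented in graphical and/or tabular form and will be summarized descriptively". It then says that, as appropriate, these statistics apply: "n, arithmetic mean, geometric mean, standard deviation, minimum, median and maximum) will be calculated for the pharmacodynamic endpoints". Protocol 10.4 sets a default for continuous variables, unless something else is stated, which includes "geometric mean with associated 95% confidence interval (CI), and the between-participant CV (%CVb) for the geometric mean".

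In SAP 7.3.1.1.1 the EPO parameters "will be listed and summarised if data is available", on absolute concentrations without baseline correction. The statistics in SAP 10.4.3 are "N, n, arithmetic mean, 95% confidence interval (CI) for the arithmetic mean, SD, median, minimum and maximum". SAP Table 5 has only an untransformed block for PD, and its Stats Analysis columns are empty. The display list has one PD parameter table, 4.2.

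For plasma PK, the same SAP section lists the geometric mean, its 95% CI, the log-scale SD and %CVb, and then an impaired:healthy geometric mean ratio with 90% CI. SAP 7.2.1.2.2 gives the model (ANOVA on logs with a cohort term) and a Hodges-Lehmann difference for Tmax.

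**The concern.** Cmax,EPO and AUC(0-t,EPO) are positive concentration parameters of the same kind as plasma Cmax and AUC. The SAP puts the plasma parameters on the log scale and leaves the EPO ones on the arithmetic scale, with no reason given, although the protocol names the geometric mean for PD.

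The objective asks about an effect of hepatic impairment, which is a between-cohort question, and the controls are matched for that purpose. If the SAP is followed exactly, the report shows per-cohort summaries, each mean with its own 95% CI, but no estimate of the difference and no interval for it. The PK result will be a ratio. The EPO result will have no prespecified counterpart on that scale, and its precision will not be visible. With 8 participants per cohort, an arithmetic mean is also sensitive to a single high value or to one cohort being more variable.

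**Working it through.** **1. Text comparison**

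| Item | Protocol | SAP, EPO parameters | SAP, plasma PK parameters |
|---|---|---|---|
| Geometric mean | Listed for PD in 10.4.2, as appropriate; also in the 10.4 default | Not in 10.4.3 | Yes |
| 95% CI and %CVb for the geometric mean | 10.4 default | Not in 10.4.3 | Yes |
| Log-scale display | – | None in Table 5; table 4.2 only | Tables 3.5 and 3.6 |
| Impaired:healthy ratio, 90% CI | Not planned for PD | Not planned | Table 3.7 |
| Tmax difference, 90% CI | Not planned for PD | Not planned | Table 3.9 |

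The first two rows are a protocol–SAP discrepancy. The last two are not, because protocol 10.4.2 plans no PD contrast either.

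The omission is recorded nowhere. The amendment log in SAP 1.1 does not mention it. It was already present in the first SAP issue, whose section 2.1 declared only the renamed or added PD parameters and no other change to the planned analysis.

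The statistics for EPO concentrations by time (table 4.1) follow a sponsor standard that is not in the documents, so geometric means there cannot be ruled out. The parameter list is explicit.

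**2. The plan's own precision figure**

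Protocol 10.2.1 gives n = 8 per cohort and log-scale SDs of 0.402 (AUC) and 0.278 (Cmax). The 90% CI at ratio 1 is exp(± t(0.95, 14) × SD × √(2/8)), with t = 1.761.

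- AUC: 1.761 × 0.402 × 0.5 = 0.354, giving (0.70, 1.42). The protocol states (0.70, 1.43); the unrounded upper limit is 1.425.
- Cmax: 1.761 × 0.278 × 0.5 = 0.245, giving (0.78, 1.28), as stated.

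The formula reproduces the plan, so it can be used for EPO.

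**3. Precision of an EPO geometric mean ratio**

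The documents give no EPO variance. The log-scale SDs 0.385, 0.5 and 0.7 are assumptions, spanning a CV of about 40% to 80% by √(exp(SD²) − 1). The CI factor is exp(1.761 × SD × 0.5).

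- SD 0.385: exp(0.339) = 1.40
- SD 0.5: exp(0.440) = 1.55
- SD 0.7: exp(0.616) = 1.85

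**4. Effect of unequal spread on a ratio of arithmetic means**

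For lognormal data the arithmetic mean is the geometric mean × exp(SD²/2). A ratio of arithmetic means is therefore the geometric mean ratio × exp((SD₁² − SD₂²)/2). With equal SDs the extra factor is 1.

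- 0.5 against 0.385: exp((0.250 − 0.148)/2) = exp(0.051) = 1.05
- 0.7 against 0.5: exp((0.490 − 0.250)/2) = exp(0.120) = 1.13
- 0.7 against 0.385: exp((0.490 − 0.148)/2) = exp(0.171) = 1.19

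Within these assumptions, a more variable cohort would look 5% to 19% higher when the geometric means are equal.

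**The case against.** The strongest reply is that PD is descriptive by design. Protocol 10.1 confines the estimation approach to the PK of daprodustat and names Cmax and AUC as the comparisons of interest. Precision is stated for those two only. Protocol 5.4 says the effect on EPO will be described. The PK objective is to compare, while the PD objective is to characterize. SAP Table 5 follows that plan faithfully. This stands: a reader might infer that the SAP removed a planned PD contrast, and the documents do not support that.

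The protocol's list also carries its own proviso about appropriateness, so the geometric mean is listed rather than required outright. The proviso readily explains leaving it off Tmax,EPO. It does not explain leaving it off Cmax,EPO and AUC(0-t,EPO), for which the SAP offers no reason.

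A reader might also infer that the objective ends with no usable information. That is too strong. SAP 10.4.3 plans medians, minima, maxima and SDs; figures 4.1 to 4.3 are linear and semi-logarithmic; listings 46 and 47 give individual values. Under a lognormal model the median estimates the geometric mean, and a ratio could be worked out afterwards. What is missing is a prespecified estimate with an interval.

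Finally, EPO is analysed uncorrected, so a ratio of absolute values mixes endogenous level with drug response. This stands as a limit on interpretation and has to be stated beside any ratio.

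**Conclusion.** Two points hold, with different standing. The omitted geometric mean for Cmax,EPO and AUC(0-t,EPO) is an unrecorded SAP inconsistency with the protocol. The lack of a prespecified between-cohort EPO estimate is inherited from the protocol; supplying one is a cheap improvement to the plan, not the correction of an SAP breach.

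The size is modest: about 5% to 19% distortion of an arithmetic-mean ratio if the cohorts differ in spread, and a 90% CI factor of 1.40 to 1.85 for a geometric mean ratio. Both rest on lognormal EPO parameters, assumed log-scale SDs of 0.385 to 0.7 and 8 participants per cohort; the CI factor also assumes a common SD.

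A reader might take exp(SD²/2), which is 8%, 13% and 28% at SDs 0.385, 0.5 and 0.7, as the bias between cohorts. It is not. Those are gaps between the two kinds of mean within one cohort, and they cancel when the SDs are equal. A 28% distortion would need no variability at all in the other cohort. Nor do the documents show that impaired participants have outlying EPO values.

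**What to change.** In SAP 7.3 (including Table 5), 10.4.3 and the display list:

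- Restore the geometric mean, with 95% CI and %CVb, for Cmax,EPO and AUC(0-t,EPO). Leave Tmax,EPO as it is. Record the change.
- Add, labelled as estimation only and for each study part separately, the impaired:healthy geometric mean ratio with 90% CI from the cohort ANOVA on logs in SAP 7.2.1.2.2. For Tmax,EPO, add the Hodges-Lehmann difference with 90% CI.
- State that the ratio is of absolute EPO and so includes endogenous level. Optionally show it also adjusted for log pre-dose EPO, which the schedule already collects and SAP Table 10 already defines as the EPO baseline.
- Align protocol 10.4.2, since it currently plans descriptive summaries only.

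The cost is wording and one extra table that can reuse the PK programs. No samples or participants are added. The downside is a wide interval on display for a secondary endpoint.
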